#### Variables

Baseline is defined as last value prior to first dose of IMP, including unscheduled visits.

Change from baseline will be calculated as follows:

• Change from baseline = post-baseline assessment value – baseline assessment value.

Duration [days] will be calculated as follows:

• Duration [days] = last observation date – first observation date + 1

#### Time from first immunization to first reaction will be calculated as follows:

Time from first immunization to first reaction [days] = first reaction date - prime immunization date + 1

**Time from first reaction to last reaction** will be calculated as follows: Time from first to last reaction [days] = last reaction date - first reaction date + 1

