### 7.1.1 Temporary discontinuation

For the Cohorts 11 to 14 (inclusive), temporary delays to the boost doses due to intercurrent illness (i.e., immunization with the boost dose within 1 wk of the scheduled day) are allowed.

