Investigational Medical Products	
 
Name: BNT162 vaccines - Anti-viral RNA vaccines for active immunization against COVID-19
 
Part A: Type: RNA-LNP vaccines utilizing different BioNTech RNA formats, i.e., uRNA (product code BNT162a1), modRNA (two variants, product codes BNT162b1 and BNT162b2) and saRNA (product code BNT162b1, BNT162b2) and saRNA (product code BNT162b1, BNT162b2 and BNT162c2 will be administered using a P/B regimen. The vaccine BNT162c2 will additionally be administered using an SD regimen.
 
Dose:
 

	The doses are detailed in the protocol Table 1, 2, 3 and 4. Dose frequency: One injection or two injections 21 days apart. Injection volumes will be up to 1.5 mL. Administration route: Intramuscular Trial subjects with the first-in-human immunization will be immunized using a sentinel dosing/subject staggering.
Treatment and Study Duration	In total, the planned trial duration for subjects is expected to be approximately 214 d for Cohorts 1 to 10, 760 d for Cohorts 11 to 13 and 214 d for Cohort 14.

	A trial subject in Cohort 11, 12, or 13 who receives a non- trial SARS-CoV-2 vaccination will be withdrawn from follow-up and discontinued from the BNT162-01 trial.
Planned Number of Subjects	For each vaccine, 12 subjects for each cohort are required in Part A for non – expansion cohorts. For the expansion cohorts, 30 subjects will be included in cohort 11, 90 subjects in cohort 12 and 30 subjects in cohort 13. 20 subjects will be included in cohort 14.
Randomization and Blinding	No randomization, open-label

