#### Analysis

Local reactions with missing time and occurring on the day of prime immunization will be assigned to all intervals starting with the prime immunization. Local reactions with missing time and occurring on the day of the boost immunization will be assigned to all intervals including the boost immunization. Local reactions with missing date will be assigned to each of the respective intervals if it cannot be ruled out, that it belongs to the time interval. The following analyses will be done for local reactions assessed by the subject, for local reactions assessed by the investigator and for both combined:

Differing from protocol section 9.4.2, the number and percentage of subjects reporting at least one local reaction in each time interval will be summarized for any local reaction and by worst grade.

The denominator of the percentages will be the number of subjects with any information on local reactions in the diary available in the respective time interval.

The number and percentage of subjects reporting at least one local reaction will be summarized by local reaction type (pain, tenderness, erythema/redness and induration/swelling) and by worst grade for each time interval. The denominator of the percentages will be the number of subjects with any information on local reactions in the diary available in the respective time interval.

The following analyses will be done for local reactions assessed by subjects:

Time after prime and after boost from

- First dose to first local reaction,
- First dose to first local reaction with grade >=3,
- First local reaction to last local reaction and
- First local reaction with grade >=3 to last local reaction with grade >= 3

will be summarized descriptively overall and by local reaction term.

The same variables will be analyzed for any reaction (local or systemic).

Moreover, the frequency of subjects with solicited local reactions and any solicited reactions within 7 days after each dose per day and the frequency of subjects with solicited local reactions within 7 days after each dose by term per day will be analyzed.

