#### Analysis

Solicited systemic reactions will be analyzed in the same way as solicited local reactions (see Section 6.4.1 of the SAP).

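### Applied as written, the SAP counts post-boost time to first solicited reaction from the prime dose, which adds each subject's prime-to-boost interval (21 days on schedule)

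*SAP*

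**What the plan says.** SAP 6.1.2 defines one onset time for solicited reactions: "Time from first immunization to first reaction [days] = first reaction date - prime immunization date + 1". Its origin is the prime immunization.

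SAP 6.4.1 uses an onset time in a block that opens "Time after prime and after boost from". The listed variables include "First dose to first local reaction" and "First dose to first local reaction with grade >=3", each summarized overall and by reaction term. The same section repeats these variables for any reaction, local or systemic. Section 6.4.2 carries them over to systemic reactions: "Solicited systemic reactions will be analyzed in the same way as solicited local reactions".

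The SAP does have a variable counted from the latest dose (days since last immunization, in 6.1.2), but it is defined on the onset date of an adverse event. SAP 6.4.1 also clarifies that the post-prime interval covers study days 1 to 8 and that the other intervals work the same way. That settles which days belong to an interval, not the day from which onset is counted. SAP Appendix 1, which lists departures from the protocol, is silent on the point.

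**The concern.** A time to first reaction after the boost is useful only if it is measured from the boost. The formula subtracts the prime date and the bullets name the first dose, yet the output is required for both doses. A subject boosted on Day 22 who reacts that day would be recorded at 22 days, while a subject who reacts on the day of the prime is recorded at 1 day.

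The post-prime and post-boost columns would then be on different scales. The post-boost column would also vary between subjects, and possibly between cohorts, partly because boosts were given on different days. The comparison is of real interest in Cohort 11, where prime and boost doses differ and tolerability is part of the rationale (Protocol 4.2).

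**Working it through.** **Inputs**
- Formula: SAP 6.1.2, quoted above.
- Planned interval: "One injection or two injections 21 days apart" (SAP 1.2). With prime on study day 1, the boost falls on Day 22.
- Visit window: Visit 4 at Day 22±2 (visit-flexibility footnotes to Protocol Tables 6, 8 and 9), so Day 20 to Day 24.
- Permitted delay for intercurrent illness, Cohorts 11 to 14 only: "immunization with the boost dose within 1 wk of the scheduled day" (Protocol 7.1.1). Taking the scheduled day as Day 22, the latest boost is Day 29.
- Solicited window: the day of immunization to day 7 after it (SAP 6.4.1).

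**Reproducing the plan's own figure.** For reactions 0 to 7 days after prime, the formula gives 1 − 1 + 1 = 1 up to 8 − 1 + 1 = 8. This matches the SAP's study days 1 to 8, so the formula is right for the prime.

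**Applying it after the boost.** Let the boost be on study day B and the reaction d days later.
- Written formula: (B + d) − 1 + 1 = B + d.
- Counted from the boost: (B + d) − B + 1 = d + 1.
- Difference: (B + d) − (d + 1) = B − 1, which is the subject's prime-to-boost interval.

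| Boost day B | Added days (B − 1) | Written formula, d = 0 to 7 | Counted from boost |
|---|---|---|---|
| 20 | 19 | 20–27 | 1–8 |
| 22 | 21 | 22–29 | 1–8 |
| 24 | 23 | 24–31 | 1–8 |
| 29 (delay, Cohorts 11–14) | 28 | 29–36 | 1–8 |

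**Spread from scheduling alone.** Same-day reactions would be reported between 20 and 24 in Cohorts 1 to 10, a spread of 24 − 20 = 4 days. In Cohorts 11 to 14 a delayed boost extends this to 29 − 20 = 9 days. Because the addition differs by subject, subtracting 21 from the finished table does not repair it.

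**Illustration on assumed inputs.** The documents give neither the distribution of boost days nor that of onset. Suppose boost days are uniform on 20 to 24, and onset is 0, 1, 2 or 3 days after boost with probability 40, 40, 15 and 5%.
- Variance of boost day: (5² − 1)/12 = 2.
- Mean onset: 0.40 + 0.30 + 0.15 = 0.85. Mean square: 0.40 + 0.60 + 0.45 = 1.45. Variance: 1.45 − 0.85² = 0.73.
- Share of variance due to scheduling: 2/(2 + 0.73) = 73%.
- Median: 23 days by the written formula, 2 days counted from the boost.

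If every boost fell exactly on Day 22, the scheduling share would be zero and the shift a constant 21 days.

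**The case against.** The strongest reply is that the formula is labelled as time from the first immunization and is correct for that quantity. Under a lead-in that separates prime from boost, the first-dose wording in the bullets may be a loose way of naming the dose that opens each period. A programmer could well count from the boost date, and a value of 22 or more for a 7-day window would be conspicuous in review. This stands as far as it goes: a reader might infer that the reported post-boost times will certainly be about 21 days too long, and the documents do not establish that. They establish that the written rule gives that result and that no other rule is written. Counting from the boost would be an undocumented departure, and two programmers could resolve it differently.

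Second, much of the dose-relative timing survives elsewhere. SAP 6.4.1 also plans the frequency of subjects with reactions on each day within 7 days after each dose, and lists all reactions. This is correct and limits the damage, although those tables do not give time to first onset.

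Third, the nine-day spread needs an early boost in one subject and an illness delay in another, and is possible only in Cohorts 11 to 14. It should not be read as describing the whole trial.

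**Conclusion.** The rule as written gives the wrong quantity after the boost: onset counted from the boost plus the prime-to-boost interval. The addition is 21 days on schedule, 19 to 23 within the visit window, and up to 28 with the permitted delay in Cohorts 11 to 14. It applies to time to first reaction and to first grade 3 or higher reaction, for local, systemic and any reactions. The size rests on a literal reading of SAP 6.1.2 and 6.4.1 and on the protocol's visit windows.

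Two stronger conclusions are tempting. One is that the post-boost values would say nothing about when the reaction began. They are a sum, so onset still contributes, but it cannot be separated from scheduling in the summary. The other is that the primary safety results are compromised. Although these summaries sit among the primary analyses, they are descriptive and no hypothesis is tested. Reaction frequencies, worst grades, per-day frequencies, first-to-last-reaction times (which use no immunization date), all post-prime results and single-dose BNT162c2 are unaffected. Dose-escalation decisions rest on the Safety Review Committee's review of 48-hour data, not on this table.

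The point should be corrected, but it does not threaten the trial's main safety description.

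**What to change.** In SAP 6.1.2, replace the onset formula with: time to first reaction after an immunization [days] = date of first reaction within that immunization's 7-day interval − date of that immunization (prime or boost) + 1. Naming the interval also makes clear that a subject who reacted after prime can have a separate first reaction after boost.

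In SAP 6.4.1, replace *First dose* with *the respective immunization* in both time-to-reaction bullets. Section 6.4.2 follows by its cross-reference.

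The cost is a few lines of SAP text and one derivation in the program. Immunization dates and times are already recorded in the case report form (Protocol 6.4), so no new data are needed. If the tables have already been produced, check which date the program used and rerun only the post-boost time-to-first-reaction summaries if it was the prime.

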#### Days since last immunization will be calculated as follows:

Days since last immunization = onset date of AE- date of last immunization+1

For conversion of days to months or years the following rules will be applied:

- 1 month = 30.25 days
- 1 year = 365.25 days

Study Day and Treatment Day are defined as follows:

- Study day:
- If study date < date of first dosing, then study day = study date date of first dosing
- $\circ$  If study date  $\geq$  date of first dosing, then study day = study date date of first dosing + 1

Fold increase will be calculated as follows:

• Fold increase = post-dose value / baseline value

#### 6.1.3. Missing Data

As a general rule, missing data will not be substituted (i.e., missing data will not be replaced but will be handled as "missing" in the statistical evaluation), with the following exception for summary analyses:

Clinical safety laboratory variables given as '<xx' will be evaluated as 0.5 \* xx in the summary tables. In the listings they will be displayed as "<xx" or similar.

#### 6.2. Subject Dispositions

For the SCR, a listing of subjects having failed screening will be presented.

Subject disposition will be listed with date of informed consent, date of screening, date of immunization and date of study completion/discontinuation.

The number and percentage of subjects in the analysis sets will be summarized by group (i.e. by vaccine type and cohort) and cohort-total for the subjects in the SAF.

For the SAF, number and percentage of subjects having prematurely discontinued the study with a summary of the primary reason (e.g., adverse events, death, withdrawal by subject, lost to follow-up), of subjects who completed the end of treatment phase (merged from End of Trial variable and from End of Treatment variable) and who completed the follow-up phase will be presented by group (i.e. by vaccine type and cohort) and cohort-total.

Subjects having prematurely discontinued will be listed with date and reason for premature discontinuation.

Subjects in the SCR but excluded from SAF, subjects in SAF but excluded from SAFB/ IMM/ IMMPP will be listed with reason for exclusion.

## 6.3. Baseline Characteristics

## 6.3.1. Demographics

Demographic and baseline variables will be summarized for subjects in the SAF analysis set. Age (calculated as Age [years] + age\_months [months] /12), weight [kg], height [cm], and body mass index (BMI) (kg/m^2) will be summarized as continuous data by group and cohort-total.

Sex (male vs female), ethnicity (Hispanic or Latino, Not Hispanic or Latino, Not reported, Unknown) and race (White, Black or African American, Asian, American Indian or Alaska Native, Native Hawaiian or Other Pacific Islander, Not reported, Unknown, Other) will be summarized as categorical data by group and cohort-total.

A listing of demography will be provided.

## 6.3.2. Concomitant Medication

Prior and concomitant medications will be defined using start and stop dates recorded, relative to the first and last dose of study medication. Any medication taken before 28 days prior to the start date of IMP will not be classified as prior or concomitant medication. A prior medication will be defined as any therapy taken 28 days prior up to (but not including) the start date of IMP. A concomitant medication will be defined as any medication either:

- Taken prior to (but not including) the start date of IMP and
  - Ongoing at the first vaccination
  - Or with a missing end date,
- Or with a start date on or after the date of the first vaccination up to 28 days after the last vaccination.

If a medication cannot be clearly assigned to prior medication due to missing dates, it will be evaluated as concomitant medication.

Medications will be coded using the WHO Global (Drug Insight) March 2020 B3 standard drug codes resulting in Anatomical-Therapeutic-Chemical (ATC) codes indicating therapeutic classification.

Listings of prior and concomitant medications will be provided.

## 6.3.3. Medical History

Medical history data will be coded using the Updated Version Medical Dictionary for Regulatory Activities (MedDRA®) coding system 23.0 including specific terms for COVID-19.

A listing of medical history data will be provided. For cohort 13 of BNT162b2 construct, a listing on transplantations and HIV will be provided.

## 6.3.4. Procedures and Non-drug Therapies

Procedures and non-drug therapies will be listed for cohort 13 of the BNT162b2 construct.

## 6.4. Primary Analyses

Hereinafter, the primary analyses for Part A are described.

The primary endpoints are solicited local reactions at the injection site, solicited systemic reactions and the proportion of subjects with at least 1 unsolicited treatment emergent adverse event (TEAE).

Clarification: Only local and systemic reactions assessed by subject will be analysed as primary endpoint. As additional analyses, the local and systemic reactions assessed by the investigator will also be included in tables displaying "worst possible grade" for data completeness.

All primary analyses will be performed using the SAF and analyses of adverse events will possibly be repeated using the SAFB.

All primary analysis endpoints will be summarized by group (i.e. by vaccine type and cohort) and all cohorts combined for each type (cohort-total).

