## 7 DISCONTINUATION OF TRIAL TREATMENT AND TRIAL SUBJECT DISCONTINUATION/WITHDRAWAL

## 7.1 Discontinuation of trial treatment

In rare instances, it may be necessary for a trial subject to permanently discontinue IMP administration (i.e., to not receive the boost dose for groups with P/B regimens). If IMP administration is definitively discontinued, the trial subject will remain in the trial to be evaluated for safety, i.e., subjects should still complete all assessments planned in the SoA (Section 1.3).

IMP administration must be stopped if dose limiting toxicities described in Section 6.6.1 are observed.

If any of the above are observed, an unscheduled safety analysis by the SRC will be required. Trial subjects who tolerated initial vaccinations will be allowed to receive a second vaccination during this time.

In the event of discontinuation of trial treatment, it must be documented on the appropriate CRF/in the medical records whether the participant is discontinuing further receipt of trial treatment or also from trial procedures, post-treatment follow-up, and/or future collection of additional information.

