#### 9.4.2 Primary endpoints

The primary endpoints are defined in Section 3.

All AEs will be coded using the most recent version of Medical Dictionary for Regulatory Activities (MedDRA®) coding system to get a system organ class (SOC) and preferred term (PT) for each AE.

Treatment-emergent AEs (TEAEs) are defined in Section 10.3.1.1 and will be summarized using the Safety Set. In general, AEs will be analyzed by group (i.e., by type [BNT162a1, BNT162b1, BNT162b2, BNT162c2 SD, and BNT162c2 P/B] and dose level) and for each immunization, i.e., for:

- Prime immunization up to 7 d after initial immunization
- Prime immunization up to boost immunization or 28 d after initial immunization (whatever comes first)
- Boost immunization up to 7 d after boost immunization (only for P/B regimens)
- Boost immunization up to 28 d after boost immunization (only for P/B regimens)
- Prime immunization up to 28 d after boost immunization or after prime immunization (if no boost was given)

Additionally, AEs will be summarized for all dose levels combined for each type.

For each analysis, the number and percentage of subjects reporting at least one AE will be summarized by PT nested within SOC for each of the following AE types using the Safety Set:

- Any AE
- Any AE excluding AEs based on solicited reporting via subject diaries
- Related AE

Clinical Trial Protocol including Amendments Nos. 01 to 09 BNT162-01 Page 83 of 113 Version: 13.0 Date: 12 JAN 2022

- Grade ≥3 AE
- Related Grade ≥3 AE
- Any SAE
- Related SAE

Moreover, the number and percentage of subjects with any AE will be summarized by worst grade by PT nested within SOC.

Local reactions and systemic reactions will be graded using criteria based on the guidance given in US FDA Guidance for Industry "Toxicity Grading Scale for Healthy Adult and Adolescent Volunteers Enrolled in Preventive Vaccine Clinical Trials" (see Section 10.3.1.11).

For each immunization, the number and percentage of subjects reporting at least one local reaction or systemic reaction (i.e., solicited data collected using subject diaries) will be summarized for each of the following types using the Safety Set:

- Any local reactions or systemic reactions
- Grade ≥3 local reactions or systemic reactions

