## 1.1. Objectives and Endpoints

Objectives	Endpoints a
Primary	
To describe the safety and tolerability profiles of prophylactic BNT162 vaccines in healthy adults after single dose (SD; prime only) or prime/boost (P/B) immunization.	
 
Solicited local reactions at the injection site (pain, tenderness, erythema/redness, induration/swelling) recorded up to 7 days (d) after each immunization (trial days 8 and 29).
 
Solicited systemic reactions (nausea, vomiting, diarrhea, headache, fatigue, myalgia, arthralgia, chills, loss of appetite, malaise, and fever) recorded up to 7 d after each immunization (trial days 8 and 29).
 
Deviating from protocol version 13.0, the endpoint related to unsolicited treatment emergent adverse events (TEAE) will be:
 
The proportion of subjects with at least 1 unsolicited treatment emergent adverse event (TEAE):         
 
o For BNT162a1, BNT162b1, BNT162b2 and BNT162c2 (P/B):
 
Occurring after prime immunization up to boost immunization or 28 d after the prime immunization (whichever comes first) and 28 d after the boost immunization.
 
o For BNT162c2 (SD):
 
 
 

Table 2: Objectives and endpoints

	The proportion of subjects with at least 1 unsolicited TEAE
	occurring up to 28 d after the immunization.
Secondary	

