#### Safety Boost Set (SAFB)

The safety boost set is defined as all subjects who received two doses of IMP (prime and boost immunization).

Note: Subjects receiving BNT162c2 as SD will be excluded from the SAFB as they receive only a prime immunization according to protocol.

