## 6.1.1. Tables and Listings

#### Tables

In general, data will be summarized by groups (i.e., by vaccine type [BNT162a1, BNT162b1, BNT162b2, BNT162c2 SD and BNT162c2 P/B] and cohort) and all cohorts combined for each type (cohort-total). Furthermore, selected cohorts may be combined. The cohorts and cohort-total will be presented in columns and the different vaccine types in different tables.

There may be additional total columns for younger (18 to 55 years) and older (56 to 85 years) subjects.

Descriptive summary tables as well as figures will be based on scheduled visits.

Continuous variables will be summarized by group using the following descriptive statistics: number of subjects with non-missing data (n), mean, standard deviation (SD), median, minimum (min) and maximum (max).

Descriptive statistics of titer and fold increase of titer will additionally include geometric mean and its two-sided 95% confidence interval (CI). The geometric mean titer (GMT) is calculated as the mean of the logarithm of the functional antibody titers, back-transformed into the original scale. Two-sided CIs will be obtained by calculating CIs using t-distribution for the mean of the logarithmically transformed assay results and transforming the limits back to the original scale.

Geometric mean fold rise (GMFR) is calculated as the mean of the difference of logarithmically transformed assay results (post vaccination time point – pre vaccination time point) and back-transformed into the original scale. Two-sided CIs will be obtained by calculating CIs using Student's t-distribution for the mean difference of the logarithmically transformed assay results and transforming the limits back to the original scale.

Categorical variables will be summarized by group presenting absolute and relative frequencies (n and %) of subjects in each category (including the category 'missing' if applicable).

Percentages will be calculated based on the number of subjects in the respective analysis set (N) as denominator if not stated differently. Percentages may be presented with exact 95% Clopper-Pearson CIs.

SDs as well as CIs will only be calculated if values of at least 3 subjects are available.

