#### **Analysis Sets**

The SCR will be used for disposition. The SAF will be used for analysis of safety and adverse events data. Some analyses of the adverse events will be repeated using the SAFB if the SAF and the SAFB sets differ. The IMM will be used for the analysis of immunogenicity data. The analyses of all vaccines may be repeated using the IMMPP if the two analysis sets differ significantly. This will be decided at the data review meeting.

If subjects by accident receive two different doses or vaccines, they will switch the group and will be displayed for each immunization with the corresponding group. For combined analyses, subjects who received two different doses will be assigned to the lower dose. Subjects who receive different doses as per protocol will be presented in their respective group.

Data of subjects who failed to complete all visits of the study (dropout or withdrawal) will be reported as far as their data is available.

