#### 6.4.3. Adverse Events

#### Definition

For detailed information on adverse events see section 10.3 of the protocol.

Adverse events (AEs) will be coded using the Updated Version MedDRA® 23.0 including specific terms for COVID-19 to get a system organ class (SOC) and preferred term (PT) for each AE.

A treatment emergent adverse event (TEAE) is defined as any AE with an onset after the first immunization (if the AE was absent before the first immunization) or worsened after the first immunization (if the AE was present before the first immunization). AEs with an onset date more than 28 days after the last immunization will be considered as treatment emergent only if assessed as related to IMP by the investigator. AEs that cannot be determined to not be treatment emergent due to missing date or time will be defined as TEAE.

Clarification: To clarify the definition in the protocol, AEs with an onset date at the date of the first immunization will only be considered as treatment emergent if the AE occurred after the first immunization.

The TEAEs will be evaluated for the following time intervals, clarifying and harmonizing the intervals defined in the protocol:

- Prime immunization up to boost immunization or day 28 (inclusive) after initial immunization (whatever comes first)
- Boost immunization up to day 28 (inclusive) after boost immunization
- All TEAEs (regardless of relationship assessment) occurring from

- Prime immunization up to day 28 after boost immunization (inclusive).
- If no boost immunization, up to 28 days (inclusive) after prime immunization
- All TEAEs assessed as related through visit 10.

The intervals starting or ending with an immunization, will start or end with the date and time of the immunization. TEAEs are assigned to the time intervals according to their start date and time. AEs with missing date will be assigned to each of the respective intervals if it cannot be ruled out, that it belongs to the time interval.

Deviating from the protocol, the time intervals including 7 days after each immunization will not be analyzed.

AEs will be evaluated for the following time interval 'After Day 28 after boost or after prime (if no boost)':

All AEs (regardless of relationship assessment) occurring

- After day 28 after boost immunization
- o If no boost immunization, after 28 days after prime immunization

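### The post-boost TEAE proportion is taken over all primed subjects, so those never boosted count as event-free and wholly unboosted cohorts come out at 0%

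*SAP*

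**What the plan says.** For prime/boost regimens, SAP 1.1 defines the unsolicited-TEAE endpoint over the period after the prime "and 28 d after the boost immunization". SAP 6.4.3 makes the second part an interval of its own, "Boost immunization up to day 28 (inclusive) after boost immunization". It asks for the number and percentage of subjects with a TEAE in each interval, including a version without diary-based events.

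The analysis set is fixed in SAP 6.4: "All primary analyses will be performed using the SAF and analyses of adverse events will possibly be repeated using the SAFB". SAP 5.1 admits to the SAF anyone with at least one dose. On denominators, SAP 6.1.1 (Tables) says: "Percentages will be calculated based on the number of subjects in the respective analysis set (N) as denominator if not stated differently". SAP 6.4.3 states nothing different. Protocol 9.4.2 also says that TEAEs "will be summarized using the Safety Set".

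A set of boosted subjects is available in SAP 5.1: "The safety boost set is defined as all subjects who received two doses of IMP (prime and boost immunization"). Its role is set in SAP 6.1.1 (Analysis Sets): "Some analyses of the adverse events will be repeated using the SAFB if the SAF and the SAFB sets differ". Neither that section nor 6.4 names the tables to be repeated.

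**The concern.** Only a boosted subject can have an event in an interval that begins at the boost. With the SAF as denominator, primed-only subjects add to N and never to the numerator, so the error is always downward.

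This has already happened in the trial. Protocol Table 1, footnote b, records that the six subjects primed in BNT162a1 Cohort 1A were not dosed on Day 22. The note to Protocol Table 2 records that the BNT162b1 60 µg boost was not given because of tolerability after the prime. SAF membership needs only one dose, so these subjects stay in N. Protocol 7.1 also keeps a subject whose IMP is discontinued under observation: "the trial subject will remain in the trial to be evaluated for safety".

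The primary objective is to describe safety and tolerability. Under the stated rule, the BNT162b1 dose whose boost was withheld for tolerability would show the lowest possible post-boost TEAE rate, and the cohort-total column would carry the dilution. The SAP does use at-risk or data-available denominators elsewhere: per interval for diary-reported reactions (6.4.1, 6.4.2) and per visit for seroconversion (6.5.3).

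There are two smaller faults of the same kind:

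- SAP 6.4.1 asks for time to first reaction after the prime and after the boost. Its list items run from the first dose, and the only onset formula in SAP 6.1.2 subtracts the prime date.
- The additional investigator-assessed and combined reaction tables in SAP 6.4.1 and 6.4.2 use subjects with diary information as denominator, so the numerator need not be a subset of it.

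**Working it through.** **Plan's own figure.** Protocol 9.2 gives the probability of seeing a TEAE of 15% incidence at least once in 12 subjects: 1 − 0.85^12 = 85.8%, which reproduces. It requires all 12 to be exposed. For the post-boost period it is 1 − 0.85^11 = 83.3% with 11 boosted, 1 − 0.85^10 = 80.3% with 10, and 0 with none.

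**Inputs**

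- Cohort 1A: 6 primed, 0 boosted (Protocol Table 1, footnote b).
- BNT162b1 60 µg: 0 boosted (note to Protocol Table 2). The number primed is not stated; the planned 12 is assumed.
- BNT162b1: at most 120 subjects in 10 cohorts (Protocol Table 5). The note to Table 2 names five younger-adult doses: 1, 10, 30 and 50 µg given as prime/boost, and 60 µg.
- All other cohorts are assumed to have 12 primed subjects, all boosted.

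**Formula.** With x events among b boosted subjects and N in the SAF, the reported rate is x/N = (x/b) × (b/N). The dilution factor is b/N. If b = 0 the true rate is not estimable, but x/N is 0.

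**Cohorts with no boost.** The exact (Clopper-Pearson) 95% upper limit for zero events is 1 − 0.025^(1/N).

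| Group | SAF result | Exact 95% CI | On boosted subjects |
|---|---|---|---|
| BNT162a1 Cohort 1A | 0/6 = 0% | 0 to 45.9% | not estimable |
| BNT162b1 60 µg | 0/12 = 0% | 0 to 26.5% | not estimable |

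**Partly boosted cohort of 12.** The factor is 11/12 = 0.917 with one unboosted, 10/12 = 0.833 with two and 9/12 = 0.75 with three. For example, 3 subjects with events among 10 boosted give 3/12 = 25.0% on the SAF and 3/10 = 30.0% on the SAFB.

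**BNT162b1 cohort-total, 12 unboosted.** The factor depends on how many cohorts ran:

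- 5 cohorts: 48/60 = 0.80
- 7 cohorts: 72/84 = 0.857
- 10 cohorts: 108/120 = 0.90

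A 30% rate among boosted subjects would appear as 30 × 0.80 = 24% to 30 × 0.90 = 27%.

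**BNT162a1 cohort-total, 6 unboosted plus k other cohorts.** The factor is 12k/(12k + 6) = 0.667, 0.80, 0.857, 0.889 and 0.909 for k = 1 to 5.

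**Onset formula.** Take a subject whose first reaction after a Day 22 boost falls on the day of that boost. Subtracting the prime date gives 22 − 1 + 1 = 22 days; subtracting the boost date gives 22 − 22 + 1 = 1 day.

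**The case against.** The strongest reply is that the plan already provides the at-risk set. SAP 6.1.1 commits to repeating some adverse-event analyses on the SAFB when the sets differ, and for these two vaccines they do; the weaker wording in 6.4 may only echo that condition. SAP 6.2 tabulates analysis-set counts by cohort and lists SAF subjects excluded from the SAFB with reasons. SAP 6.7.1 adds a compliance summary. A careful reader would see that nobody in the 60 µg group was boosted. All of this stands as mitigation. It does not say which tables are repeated, and the lead percentage and cohort-total remain on the SAF.

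Further points:

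- **Display.** No table shells are available, and a programmer might leave the cell blank; confidence intervals are also optional. That is possible, but the text does not instruct a blank, and blanking one cohort would not correct cohort-total.
- **Endpoint reading.** SAP 1.1 could mean one proportion over both periods, for which the SAF is right. SAP 6.4.3 nevertheless requires a separate post-boost percentage.
- **Protocol.** The SAF follows Protocol 9.4.2. That is true, and SAP 7.1 exists to record such departures.
- **Cohort-total factors.** These rest on assumed cohort counts. The Table 2 note draws on two trials, and BNT162a1 dosing was deferred. The point is accepted, and the figures are therefore given as ranges.
- **Weight.** The trial is descriptive, and dose-progression decisions use 48 h data, not this table. This limits the consequence, but in a descriptive trial the percentage is itself the result.
- **Smaller faults.** The onset problem needs a literal reading of the formula, and the diary-denominator problem arises only when an investigator records a reaction for a subject with no diary information in that interval. Both are minor.

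**Conclusion.** The concern holds: the rule is wrong as written for TEAE intervals that start at the boost, and it should be fixed. The conclusion follows from the SAF definition, the default denominator and the absence of an override in SAP 6.4.3. It needs no assumption about event rates.

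The direction is always downward. The well-supported sizes are a 0% figure where nothing can be estimated in the two unboosted groups, and a general factor of boosted/primed. The cohort-total factors (0.80 to 0.90 for BNT162b1, 0.667 to 0.909 for BNT162a1) depend on 12 primed per cohort, except 6 in Cohort 1A, and on how many cohorts ran, which the documents do not state.

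The prime interval, the overall interval, the BNT162c2 single-dose groups, fully boosted cohorts and the percentages of subjects with diary-reported reactions are unaffected.

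**What to change.** 1. In SAP 6.4 and 6.4.3, make the SAFB the main denominator for every TEAE interval starting at the boost, including cohort-total, and show not applicable where no subject was boosted. Keep the SAF for the prime and overall intervals. Bring the SAFB statements in 6.1.1 and 6.4 into line, and record the departure from Protocol 9.4.2 in SAP 7.1.
2. In SAP 6.1.2, add a post-boost onset formula: first post-boost reaction date minus boost date plus 1.
3. In SAP 6.4.1, and through it 6.4.2, base the investigator-assessed reaction tables on subjects with investigator data, and the combined tables on subjects with data from either source.

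The main change costs SAP wording, one entry in 7.1 and a re-run of the post-boost TEAE tables. Items 2 and 3 also mean re-running the affected reaction tables. No new data are needed, and post-boost TEAE percentages rise only in groups that contain unboosted subjects.
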